9.4.1. Primary Analyses

Profiles for DLco will be summarized and presented graphically by treatment group as appropriate for the data. The change from baseline in DLco at Day 4, Day 5 and Day 7 will be calculated and summarized in tabular format and/or graphically by treatment. For the change from baseline in DLco, a statistical analysis will be performed using a mixed effect model with repeated measures with a fixed effect term for treatment, period and day, with a random effect for subject, day in the repeated statement with subject being subject by period, and baseline as a covariate, if data permit. Point estimates and associated 95% confidence intervals will be constructed for the differences between the active treatment and placebo.

Full details of analysis will be specified in the RAP.

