9.4.2. Secondary Analyses

For other diffusing capacity pharmacodynamic (PD) endpoints such as DLno, D_M and V_c , similar analyses as in Section 9.4.1 will be provided, as data permit. For these PD endpoints, which may be \log_e transformed prior to analysis to satisfy model assumptions, point estimates and their associated 95% confidence intervals will be back-transformed to provide point estimates and 95% confidence intervals for the ratios.

For pulmonary function measurement endpoints such as FVC, FEV1, FEF_{25-75} FEF_{50} , and FEF_{75} , FRC and EELV, similar analysis as in Section 9.4.1 will be provided, as data permit. For these PD endpoints, which may be \log_e transformed prior to analysis to satisfy model assumptions, point estimates and their associated 95% confidence intervals will be back-transformed to provide point estimates and 95% confidence intervals for the ratios.

For respiratory rate measurement and dyspnea score, similar analysis as in Section 9.4.1 will be provided, as data permit.

In terms of DLco and DLno changes from baseline after saline challenge on Day 5 and after exercise on Day 7, the change from baseline for the challenge (after-before) will be calculated and summarized in tabular format by treatment. A statistical analysis will be performed using a mixed effect model with a fixed effect term for treatment, period and sequence, random effect term for subject-within-sequence, and baseline as a covariate, if data permit. Point estimates and associated 95% confidence intervals will be constructed for the differences between the active treatment and placebo.

In terms of ventilatory efficiency, scatter plots for Ve/VCO₂ at Baseline and Day 7 will be performed and the slope or correlation of Ve/VO₂ provided. Summary statistics for Ve and VCO₂ and change from baseline measurement will be provided.

Details on the analysis of other endpoints will be provided in RAP.

Pharmacokinetic analyses will be the responsibility of the Clinical Pharmacology Modeling & Simulation Department within GlaxoSmithKline. Plasma GSK2798745 concentration-time data will be analyzed by non-compartmental methods with the latest available version of WinNonlin software. Calculations will be based on the actual sampling times recorded during the study. From the plasma concentration-time data, the pharmacokinetic parameters such as Cmax and AUC may be determined, as data permit.

The details of the PK analysis will be listed in the RAP.

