3. SUMMARY OF KEY PROTOCOL INFORMATION

3.1. Changes to the Protocol Defined Statistical Analysis Plan

There were no changes or deviations to the originally planned statistical analysis specified in the protocol amendment 02 (Dated: 19-APR-2016).

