9. SECONDARY STATISTICAL ANALYSES

9.1. Efficacy Analyses

9.1.1. Overview of Planned Efficacy Analyses

The secondary efficacy analyses will be based on the “Analysis Population”, unless otherwise specified.

The study is being conducted at two sites. One of these two sites does not have the ability to collect DLno, DM, and Vc. Summaries of DLno, DM, and Vc will only be performed for subjects at the site which this data is collected.

When calculating summary statistics for efficacy data, pooled summaries and summaries for each site individually will be generated. Patient ID's in the PPD are from the Mayo Clinic and patients ID's in the PPD are from Hennepin.

[Table 4](#) provides an overview of the planned efficacy analyses with further details of data displays being presented in [Appendix 11: List of Data Displays](#).

All change from baseline table, listing, and figures, use the baseline measured just prior to the period, (i.e. period 1 measurements use the baseline measured just prior to period 1 and period 2 measures use the baseline measured just prior to period 2), unless otherwise specified.

Statistical analysis (adjusted means and/or posterior means) will be performed on secondary endpoints as shown in Table 4

Table 4 Overview of Planned Efficacy Analyses

Endpoint	Absolute						Change from Baseline					
	Stats Analysis		Summary		Individual		Stats Analysis		Summary		Individual	
	T	F	T	F	F	L	T	F	T	F	F	L
Diffusing capacity for nitric oxide (DLno)	Y		Y	Y	Y	Y			Y	Y	Y	Y
Membrane conductance (DM)	Y		Y	Y	Y	Y			Y	Y	Y	Y
Capillary blood volume (Vc)	Y		Y	Y	Y	Y			Y	Y	Y	Y
Dm/Vc	Y		Y		Y				Y			
Diffusing capacity for carbon monoxide (DLco) following exercise			Y	Y	Y	Y			Y	Y	Y	Y
Diffusing capacity for carbon monoxide (DLco) following saline infusion			Y	Y	Y	Y			Y	Y	Y*	Y
VE/VCO ₂ ratio			Y	Y	Y	Y			Y	Y	Y	Y
Forced vital capacity (FVC)			Y	Y	Y	Y			Y	Y		Y
Forced expiratory volume in 1 second (FEV1)			Y	Y	Y	Y			Y	Y		Y
Forced expiratory flow, FEF25-75			Y	Y	Y	Y			Y	Y		Y
Forced expiratory flow, FEF50			Y	Y	Y	Y			Y	Y		Y
Forced expiratory flow, FEF75			Y	Y	Y	Y			Y	Y		Y
Respiratory rate (Preventice Body Guardian)			Y	Y	Y							
Troponin			Y			Y			Y			Y
SF-36 acute score			Y			Y			Y	Y		
Dyspnea score			Y			Y			Y	Y		Y

*Change from value is calculated by taking the post-saline measure to the prior saline measure

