2.09	Analysis	Non-Standard EFF_T8	Summary Statistics of VE/VCO ₂ Ratio Change from Baseline	VE/VCO ₂ ratio has measures on Baseline and Day 7 before and after 3-minutes step test. Create this table twice, one table with all patients and another table with Hennepin patients excluded from the statistics.	SAC [2]
Pulmonary Function					
2.10	Analysis	Non-Standard EFF_T4	Summary Statistics of Pulmonary Function Tests	Pulmonary function (FVC, FEV ₁ , FEF ₂₅₋₇₅ , FEF ₅₀ , FEF ₇₅) has measures on Baseline, Day 4 and Day 7 for each treatment period. Pool all patients.	SAC [2]
2.11	Analysis	Non-Standard EFF_T5	Summary Statistics of Pulmonary Function Tests Change from Baseline	Pulmonary function (FVC, FEV ₁ , FEF ₂₅₋₇₅ , FEF ₅₀ , FEF ₇₅) has measures on Baseline, Day 4, and Day 7 for each treatment period. Pool all patients.	SAC [2]
2.12	Analysis	Non-Standard EFF_T4	Summary Statistics of Pulmonary Function Tests by Site	Pulmonary function (FVC, FEV ₁ , FEF ₂₅₋₇₅ , FEF ₅₀ , FEF ₇₅) has measures on Baseline, Day 4 and Day 7 for each treatment period. Create this table twice, one table with Mayo patients and another table with Hennepin patients.	SAC [2]

Efficacy Tables					
No.	Population	IDSL / TST ID / Example Shell	Title	Programming Notes	Deliverable [Priority]
2.13	Analysis	Non-Standard EFF_T5	Summary Statistics of Pulmonary Function Tests Change from Baseline by Site	Pulmonary function (FVC, FEV ₁ , FEF ₂₅₋₇₅ , FEF ₅₀ , FEF ₇₅) has measures on Baseline, Day 4, and Day 7 for each treatment period. Create this table twice, one table with Mayo patients and another table with Hennepin patients.	SAC [2]
Dyspnea					
2.14	Analysis	Non-Standard EFF_T9	Summary Statistics Dyspnea Score	Dyspnea Score has measures at Baseline pre and post exercise, Day 5 pre-saline sitting and supine, Day 7 pre and post exercise for each treatment period and at follow-up pre and post exercise	SAC [2]
2.15	Analysis	Non-Standard EFF_T5	Summary Statistics Change from Baseline Dyspnea Score	Dyspnea Score change from baseline has measures at Baseline post exercise, Day 5 pre-saline sitting and supine, Day 7 pre and post exercise for each treatment period and at follow-up pre and post exercise	SAC [2]
SF-36 score					
2.16	Analysis	SF2	Summary Statistics SF-36 Score	SF-36 Score has measures at Baseline and Day 7 for each treatment period and follow-up. Add additional rows for questions 3a to 3j to be looked at along with the domain scores	SAC [2]

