No.	Population	IDSL / TST ID / Example Shell	Title	Programming Notes	Deliverable [Priority]
2.48	Analysis	Non-Standard EFF_F14	Mean (95% CI) Change from Baseline Plot of VE/VCO ₂	Mean values of the points calculated for previous plot	SAC[2]
2.49	Analysis	Non-Standard EFF_F15	Plot of VE/VCO ₂ Change from Rest	Has 5 measures at baseline and Day 7 for each treatment along with follow-up. Bars represent the difference between the time measure and rest within a day and treatment. The number is the difference between the active and placebo bars.	SAC[2]
2.50	Analysis	Non-Standard EFF_F16	Mean (95% CI) Plot of VE/VCO ₂ Change from Rest	Has means at Day 7	SAC[2]
Pulmonary Function					
2.51	Analysis	Non-Standard EFF_F17	Spaghetti Plot of FVC	FVC has means at Baseline, Day 4 and Day 7 for each treatment and a follow-up measure	SAC[2]
2.52	Analysis	Non-Standard EFF_F18	Mean (95% CI) Plot of FVC	FVC has means at Baseline, Day 4 and Day 7 for each treatment and a follow-up measure	SAC[2]
2.53	Analysis	Non-Standard EFF_F19	Mean (95% CI) Plot of FVC Change from Baseline	FVC has means at Day 4 and Day 7	SAC[2]
2.54	Analysis	Non-Standard EFF_F17	Spaghetti Plot of FEV ₁	FEV ₁ has means at Baseline, Day 4 and Day 7 for each treatment and a follow-up measure	SAC[2]
2.55	Analysis	Non-Standard EFF_F18	Mean (95% CI) Plot of FEV ₁	FEV ₁ has means at Baseline, Day 4 and Day 7 for each treatment and a follow-up measure	SAC[2]

Efficacy Figures					
No.	Population	IDSL / TST ID / Example Shell	Title	Programming Notes	Deliverable [Priority]
2.56	Analysis	Non-Standard EFF_F19	Mean (95% CI) Plot of FEV ₁ Change from Baseline	FEV ₁ has means at Day 4 and Day 7.	SAC[2]
2.57	Analysis	Non-Standard EFF_F17	Spaghetti Plot of FEF ₂₅₋₇₅	FEF ₂₅₋₇₅ has means at Baseline, Day 4 and Day 7 for each treatment and a follow-up measure	SAC[2]
2.58	Analysis	Non-Standard EFF_F18	Mean (95% CI) Plot of FEF ₂₅₋₇₅	FEV ₂₅₋₇₅ has means at Baseline, Day 4 and Day 7 for each treatment and a follow-up measure	SAC[2]
2.59	Analysis	Non-Standard EFF_F19	Mean (95% CI) Plot of FEF ₂₅₋₇₅ Change from Baseline	FEF ₂₅₋₇₅ has means at Day 4 and Day 7	SAC[2]
2.60	Analysis	Non-Standard EFF_F17	Spaghetti Plot of FEF ₅₀	FEF ₂₅₋₇₅ has means at Baseline, Day 4 and Day 7 for each treatment and a follow-up measure	SAC[2]
2.61	Analysis	Non-Standard EFF_F18	Mean (95% CI) Plot of FEF ₅₀	FEF ₅₀ has means at Baseline, Day 4 and Day 7 for each treatment and a follow-up measure	SAC[2]

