[figure not shown]

NOTE: Plot adjusted accordingly to study data, text values are the mean change from baseline.

Example : EFF_F24
 Protocol : 201881
 Population : All Subjects

Page 1 of X

Figure 1.24
 DLco Saline Challenge Graph

NOTE: Plot adjusted accordingly to study data. The text is the difference between before and after and the percent change

Example : EFF_T1
 Protocol : 201881
 Population : Analysis

Page 1 of X

Table 1.01
 Summary Statistics of DLco

Visit	Treatment	N	n	Mean	SD	Mean Percent Predicted	Percent Predicted SD
	Screen	X	X	XX.X	XX.XX	XX.X	XX.XX
	Baseline	A	X	X	XX.X	XX.XX	
Baseline after exercise	A	X	X	XX.X	XX.XX		
	Day 4	A	X	X	XX.X	XX.XX	
	Day 5	A	X	X	XX.X	XX.XX	
Day 5 after saline infusion	A	X	X	XX.X	XX.XX		
	Day 7	A	X	X	XX.X	XX.XX	
	Day 7 after exercise	A	X	X	XX.X	XX.XX	
	Baseline	B	X	X	XX.X	XX.XX	
Baseline after exercise	B	X	X	XX.X	XX.XX		
	Day 4	B	X	X	XX.X	XX.XX	
	Day 5	B	X	X	XX.X	XX.XX	
Day 5 after saline infusion	B	X	X	XX.X	XX.XX		
	Day 7	B	X	X	XX.X	XX.XX	
	Day 7 after exercise	B	X	X	XX.X	XX.XX	
	Follow-up	NA	X	X	XX.X	XX.XX	

Example : EFF_T2
 Protocol : 201881
 Population : Analysis

Page 1 of X

Table 1.02
 Summary Statistics of DLco Change from Baseline

Visit	Treatment	N	n	Mean	SD
Baseline after exercise	A	X	X	XX.X	XX.XX
	Day 4	X	X	XX.X	XX.XX
	Day 5	X	X	XX.X	XX.XX
Day 5 after saline infusion	A	X	X	XX.X	XX.XX
	Day 7	X	X	XX.X	XX.XX
	Day 7 after exercise	X	X	XX.X	XX.XX
Baseline after exercise	B	X	X	XX.X	XX.XX
	Day 4	X	X	XX.X	XX.XX
	Day 5	X	X	XX.X	XX.XX
Day 5 after saline infusion	B	X	X	XX.X	XX.XX
	Day 7	X	X	XX.X	XX.XX
	Day 7 after exercise	X	X	XX.X	XX.XX

Example : EFF_T3
 Protocol : 201881
 Population : Analysis

Page 1 of X

Table 1.03
 Summary Statistics of DLno

Visit	Treatment	N	n	Mean	SD
	Screen	X	X	XX.X	XX.XX
	Baseline	A	X	XX.X	XX.XX
Baseline after exercise	A	X	X	XX.X	XX.XX
	Day 4	A	X	XX.X	XX.XX
	Day 5	A	X	XX.X	XX.XX
Day 5 after saline infusion	A	X	X	XX.X	XX.XX
	Day 7	A	X	XX.X	XX.XX
Day 7 after exercise	A	X	X	XX.X	XX.XX
	Baseline	B	X	XX.X	XX.XX
Baseline after exercise	B	X	X	XX.X	XX.XX
	Day 4	B	X	XX.X	XX.XX
	Day 5	B	X	XX.X	XX.XX
Day 5 after saline infusion	B	X	X	XX.X	XX.XX
	Day 7	B	X	XX.X	XX.XX
Day 7 after exercise	B	X	X	XX.X	XX.XX
	Follow-up	NA	X	XX.X	XX.XX

Example : EFF_T4
Protocol : 201881
Population : Analysis

Page 1 of X

Table 1.04
Summary Statistics of FVC

Visit	Treatment	N	n	Mean	SD
Baseline	A	X	X	XX.X	XX.XX
Day 4	A	X	X	XX.X	XX.XX
Day 7	A	X	X	XX.X	XX.XX
Baseline	B	X	X	XX.X	XX.XX
Day 4	B	X	X	XX.X	XX.XX

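### The SAP specifies no active-minus-placebo estimate for spirometry or dyspnea, although the protocol plans a crossover model for both and the SAP declares no change

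*SAP*

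**What the plan says.** **Protocol.** Section 9.4.2 covers FVC, FEV1, FEF25-75, FEF50 and FEF75 in a sentence that ends "FRC and EELV, similar analysis as in Section 9.4.1 will be provided, as data permit". It then adds: "For respiratory rate measurement and dyspnea score, similar analysis as in Section 9.4.1 will be provided, as data permit". The analysis referred to, in 9.4.1, is a mixed model "with a fixed effect term for treatment, period and day, with a random effect for subject", with baseline as a covariate. Its output is the difference between active and placebo with a 95% CI.

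**SAP.** Section 9.1.1 states: "Statistical analysis (adjusted means and/or posterior means) will be performed on secondary endpoints as shown in Table 4". In Table 4 the statistical-analysis cells are filled only for DLno, DM, Vc and Dm/Vc. They are blank for the five spirometry measures and for dyspnea. The notes to SAP Table 3 define that column as formal modelling.

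Appendix 11 lists the following for these endpoints:
- summary tables 2.10 to 2.15, for example "Summary Statistics of Pulmonary Function Tests Change from Baseline";
- mean plots such as "Mean (95% CI) Plot of FVC Change from Baseline";
- spaghetti plots and by-subject listings;
- one forest plot of spirometry (Figure 2.66, shell EFF_F23), whose note says "text values are the mean change from baseline".

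The only model-results table is 2.04, for DLco.

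SAP 3.1 says: "There were no changes or deviations to the originally planned statistical analysis".

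**The concern.** Effects on pulmonary function and on dyspnea are declared secondary objectives. Protocol 4.4 chose the crossover so that each subject is his or her own control. If the SAP is followed as written, the tables report each treatment separately, and nothing in the text calls for the quantity that answers the objective.

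Two misreadings become possible. A change from baseline on active may be taken as a drug effect without subtracting the change on placebo. Or two separate intervals may be compared by eye, with no pairing and no period adjustment, and an effect that the design could show may be missed.

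Spirometry deserves particular care. SAP 8.1.2 says DLco cannot be pooled across the two sites, and one site cannot collect DLno, DM or Vc. Spirometry is pooled over both sites in Tables 2.10 and 2.11, so every completing subject could contribute to its treatment contrast.

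**Working it through.** **1. Protocol and SAP side by side**

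| Endpoint | Protocol 9.4.2 | SAP Table 4 and Appendix 11 |
|---|---|---|
| FVC, FEV1, three FEF measures | 9.4.1-type model, data permitting | No modelling marked. By-treatment N, n, mean, SD; mean (95% CI) and spaghetti plots; listings; forest plot of unclear content |
| Dyspnea score | 9.4.1-type model, data permitting | No modelling marked. Shell EFF_T9 adds median, range, percent improved by at least 1 point and score frequencies. No forest plot |
| Respiratory rate | 9.4.1-type model, data permitting | No modelling marked. Summary and individual displays |
| DLco after exercise or saline | Mixed model, active minus placebo with 95% CI | No modelling marked. Descriptive displays |
| FRC, EELV | 9.4.1-type model, data permitting | No row in Table 4 and no display |

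The SAP does not cite insufficient data as a reason for any of these reductions. The shell needed for a treatment difference already exists (EFF_T6: adjusted mean for each treatment, difference, 95% CI) but is assigned only to DLco.

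**2. The study was sized on the within-subject difference**

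The inputs are from Protocol 9.2 and 9.2.2: n=12, effect 2.3, two-sided alpha 0.05. The formula is SE = SDw × √(2/12) with 10 df, where t(0.975, 10) = 2.228. Power comes from the noncentral t distribution.

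| SDw | SE | Half-width (stated) | Power (stated) |
|---|---|---|---|
| 1.5 | 0.612 | 1.364 (1.36) | 92.2% (more than 90%) |
| 1.9 | 0.776 | 1.728 (1.73) | 76.2% (76%) |
| 2.4 | 0.980 | 2.183 (2.2) | 56.3% (56%) |

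The protocol's figures reproduce as a paired crossover contrast. They concern DLco only; neither document gives a variance for spirometry or dyspnea.

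**3. What might be lost without the paired contrast**

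This is an illustration on assumed inputs. Take SD 1 on each treatment and correlation ρ between a subject's two values, with n=12.
- Paired SE = √(2(1−ρ)/12), 10 df.
- Independent-groups SE = √(2/12) = 0.408, 22 df, t(0.975, 22) = 2.074.

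Fix the effect at which the paired contrast has 90% power, which is 3.604 paired SEs. At ρ = 0.5 the paired SE is 0.289, so the effect is 3.604 × 0.289 = 1.04. The unpaired noncentrality is then 1.04/0.408 = 2.55, which gives 68% power.

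| Assumed ρ | Power if treated as independent | Half-width ratio, independent to paired |
|---|---|---|
| 0 | 93% | 0.93 |
| 0.1 | 90% | 0.98 |
| 0.3 | 82% | 1.11 |
| 0.5 | 68% | 1.32 |
| 0.7 | 47% | 1.70 |
| 0.8 | 34% | 2.08 |

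The low end of the range matters. The SAP's change-from-baseline displays subtract each period's own baseline. Under a simple random-subject model with independent errors, the subject effect cancels and the two changes have ρ = 0. Higher values apply to the absolute-value displays, or to changes if subjects differ consistently in how they change over a period.

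**The case against.** The strongest reply has four parts.

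*The protocol's promise was conditional, and this is a small estimation study.* Development in heart failure was stopped, and SAP 4.1 records that only one more patient was to be enrolled after the prediction on 10. Protocol 9.4.2 also leaves detail on other endpoints to the analysis plan. Descriptive reporting could be a reasonable choice in that setting. This stands as a reason why a change might be acceptable. It does not explain why SAP 3.1 records none.

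*Dyspnea is a 5-point ordinal score.* A linear mixed model on it in about a dozen subjects is debatable, and EFF_T9's frequencies and percent improved are sensible summaries. This stands, and it is why the fix asks less for dyspnea. Those summaries are still by treatment and give no difference.

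*A reader might infer that active and placebo are never compared within subject.* The documents do not support that for spirometry. The image for shell EFF_F23 is not shown, and its note defines the printed text values, not the plotted estimate, so Figure 2.66 could show paired differences. Spaghetti plots and listings also show each subject's data in both periods, although they estimate no difference.

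*A reader might also infer a definite loss of power.* The SAP plans no independent-groups test and no rule based on overlapping intervals. The comparator in the illustration is therefore hypothetical, and at ρ = 0 there is no loss. This stands in full.

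**Conclusion.** The concern holds as a gap in specification together with an undeclared departure. For five spirometry measures and the dyspnea score, the protocol plans, where the data permit, a crossover model with an active-minus-placebo interval. The SAP text specifies no such estimate, does not invoke the data condition, and declares no change. For dyspnea the omission is clear from the table shells and display list. For spirometry one display, Figure 2.66, remains ambiguous.

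The consequence that needs no assumption is that two declared secondary objectives have no specified randomised contrast. Any loss of precision from comparing separate intervals runs from none at ρ = 0 upward as ρ rises. It rests on a correlation that the documents do not give, so no single power figure should be quoted.

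The same gap affects respiratory rate and post-challenge DLco, and FRC and EELV drop out of the SAP's planned analyses and displays altogether.

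**What to change.** 1. In SAP Table 4, mark statistical analysis of change from baseline for FVC, FEV1, FEF25-75, FEF50 and FEF75.
2. Add one table in the EFF_T6 layout with the adjusted active-minus-placebo difference and 95% CI for each measure. Use the protocol's crossover model with the period-specific baseline and both sites pooled. A site term is not needed: site is constant within a subject and drops out of a complete-pair contrast.
3. For dyspnea, report at least the within-subject active-minus-placebo difference with 95% CI beside the planned frequencies.
4. State that Figure 2.66 plots the active-minus-placebo difference, and relabel its text values to match.
5. For respiratory rate, post-challenge DLco, FRC and EELV, either restore the protocol's analysis or record its removal in SAP 3.1 with the reason. The same applies if the spirometry or dyspnea model is dropped on purpose.

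The cost is SAP wording, one added table, a short dyspnea addition and a relabelled figure, with no new data or subjects. The downside is a few more secondary estimates without multiplicity adjustment, which SAP section 6 already accepts for the whole plan.

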9.2. Safety Analyses

9.2.1. Overview of Planned Analyses

The safety analyses will be based on the “All Subjects” population, unless otherwise specified.

Table 5 provides an overview of the planned analyses with further details of data displays being presented in [Appendix 11: List of Data Displays](#).

Table 5 Overview of Planned Safety Analyses

Endpoint	Absolute				Change from Baseline			
	Summary		Individual		Summary		Individual	
	T	F	F	L	T	F	F	L
Exposure								
Extent of Exposure	Y			Y				
Adverse Events								
All AE's ^[1]	Y			Y				
Common AE's	Y							
All Drug-Related AE's	Y			Y				
Serious AE's	Y			Y				
Withdrawal AE's	Y			Y				
C-SSR				Y				
SNAQ				Y				
Audiometry				Y				
Laboratory Values								
Clinical Chemistry ^{[2] [3]}	Y			Y	Y			Y
LFT's	Y			Y				
Hematology /Coagulation ^{[2] [3]}				Y	Y			Y
ECG's								
ECG Findings	Y			Y				
ECG Values					Y			
Vital Signs								
Vitals Values	Y			Y	Y			Y

Endpoint	Absolute				Change from Baseline			
	Summary		Individual		Summary		Individual	
	T	F	F	L	T	F	F	L

NOTES :

- T = Table, F = Figure, L = Listing, Y = Yes display generated.
- Stats Analysis = Represents TFL related to any formal statistical analyses (i.e. modelling) conducted.
- Summary = Represents TFL related to any summaries (i.e. descriptive statistics) of the observed raw data.
- Individual = Represents FL related to any displays of individual subject observed raw data.
- 1. Listings will include subject's numbers for individual AE's & AE system organ classes, preferred terms and verbatim text.
- 2. Chemistry & haematology summaries will include both changes from baseline & results by PCI criteria.
- 3. Listings of chemistry and haematology data for subjects with abnormalities of PCI will be listed.
- 4. Urinalysis summaries will include changes from baseline results by dipstick categories.

